To describe in each study group the incidence of RSV LRTI hospitalization and all-cause LRTI hospitalization in UK reconsented participants from D366 to D731	 Incidence of RSV LRTI hospitalization Incidence of hospitalization for all-cause LRTI 				

Overall Design

Type of design	Open-label, multi-center, parallel 2-arm study: nirsevimab compared to no preventive RSV intervention					
Phase	IIIb					
Control method	Comparison to no preventive intervention					
Study population	Healthy infants born ≥ 29 weeks gestational age (WGA) entering their first RSV season and not eligible for palivizumab (born either in-season or out-of-season)					
Countries	France, Germany, and the United Kingdom					
Level and method of blinding	Open-label					
Study intervention assignment method	 Randomization will be stratified by the following: Country Age group at time of randomization (ie, age ≤ 3.0 months, age > 3.0 to ≤ 6.0 months, age > 6.0 months) 					

Brief Summary

The purpose of this study is to determine the efficacy and safety of a single intramuscular (IM) dose of nirsevimab, compared to no intervention, for the prevention of hospitalizations due to

LRTI caused by confirmed RSV infection (henceforth referred to as RSV LRTI hospitalizations) in all infants under 12 months of age who are not eligible to receive palivizumab.

Study Duration: 12 months post-dosing/randomization for France, Germany, and UK non-reconsented participants, 24 months post-dosing/randomization for UK reconsented participants. D01 will be the day of randomization (both study groups) and immunization (nirsevimab group).

Treatment Duration: 1 IM injection

Study Calendar:

- Planned date of first participant in: 01 September 2022
- Planned date of last participant in: 28 February 2023
- Planned date of last visit last participant: 28 February 2025

Note: As much as operationally feasible, the date of inclusion of the first participant will be aligned with the beginning of the RSV season. It is thus possible that the first participants are enrolled earlier than 01 September 2022.

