5.2.3.2. Missing or Partial Dates for Adverse Event and Prior / Concomitant Medication

Missing and / or incomplete dates for medications and AEs are imputed in a manner resulting in the earliest onset or the longest duration during the Treatment Period, whilst ensuring that

the start date does not occur after the stop date. The stop date will not be imputed if the medication or AE is “Ongoing”. Technically, this will be done as follows:

For a missing / incomplete start date the earliest date of the following will be imputed:

- The later date of: the earliest possible start date, and the date of the randomization (for no intervention group) / immunization (for nirsevimab group)
- The latest possible start date
- The latest possible stop date

For a missing / incomplete stop date the latest date of the following will be imputed:

- The earlier date of the latest possible stop date and the date of last dose of treatment
- The earliest possible stop date
- The earliest possible start date

Here, the earliest possible date is defined as:

- The date itself if available
- The date of the first day of the month, if month and year are available but the day is missing
- The date of the first day of the year, if year is available but day and month are missing
- The day of informed consent, if the date is completely missing

The latest possible date is defined as:

- The date itself if available
- The date of the last day of the month, if month and year are available but the day is missing
- The date of the last day of the year, if year is available but day and month are missing
- The date of last known date on the study for the participant plus one year, if the date is completely missing

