6.4.3. Prior and Concomitant Medications

All medications will be coded using the WHO Drug Global Dictionary, Format B3 (Version March 2022), Anatomical Therapeutic Chemical (ATC) Classification codes.

Concomitant medications will be collected in the event of an AE. Reportable medications include medications that may affect the interpretation of safety data (eg, an antipyretic or analgesic that could have reduced the intensity or frequency of an AE).

All vaccines administered within 14 days before or after dosing/randomization should be reported as concomitant therapies. All medications administered within 14 days before or after admission of LRTI hospitalization will also be considered as reportable.

Reportable medications will be collected in the eCRF. Dosage, homeopathic medication, topical and inhaled steroids, as well as topical, ophthalmic, and ear treatments will not be recorded (except topical analgesics applied at the injection site of study intervention).

Prior medications and concomitant medications are defined as follows:

- Prior medications are those taken prior to screening with a stop date prior to the date / time of randomization (for no intervention group) / immunization (for nirsevimab group)
- Concomitant medications are those with a start date on or after the date / time of randomization (for no intervention group) / immunization (for nirsevimab group), or those with a start date before the date / time of randomization (for no intervention group) / immunization (for nirsevimab group) and either a stop date on or after the date / time of randomization (for no intervention group) / immunization (for nirsevimab group), or are ongoing at the end of the study

See Section 5.2.3 for imputation of missing or partial dates for medication.

Prior and concomitant medications will be summarized separately for the All Randomized Set by treatment group and overall as follows:

- The number and percentage of participants with at least one prior / concomitant medication will be presented
- The number and percentage of participants with at least one prior / concomitant medication within each Anatomical Group (ATC Level 1), Therapeutic Subgroup (ATC Level 2), Pharmacological or Therapeutic Subgroup (ATC4) and preferred term will be presented. The summary will be sorted using numerical counts by descending

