order of Anatomical Group, then descending order of Therapeutic Subgroup, then descending order of preferred term in the total column. Where groups or terms tie these will be sorted alphabetically

In addition, the same type of tables (by ATC Level 1, ATC Level 2, ATC Level 4 and preferred term) will be provided for:

- All Concomitant Medications in participants who received Beyfortus as a routine medication if there are at least 10 concerned participants;
- All Vaccines given within 14 days before or after dosing/randomization;
- All Vaccines given within 14 days before or after dosing/randomization in participants who received Beyfortus as a routine medication if there are at least 10 concerned participants;
- Vaccines given within 14 days before or after dosing/randomization, restricted to the list in Appendix 2 (Section 8.2);
- Medications administered within 14 days before or after an LRTI hospital admission. The following medications will be considered for the analysis:
 - o medications with a start date within 14 days before or after an LRTI hospital admission,
 - o medications with a start date 14 days before an LRTI hospital admission but with a stop date within the 14 days before or after an LRTI hospital admissions
 - o medications with a start date 14 days before an LRTI hospital admission and still ongoing (no stop date)
- Medications administered within 14 days before or after an LRTI hospital admission in participants who received Beyfortus as a routine medication if there are at least 10 concerned participants;

Prior medications and concomitant medications will be listed separately for the All Randomized Set. In the listings, the relative start and stop day of prior / concomitant medication use will be calculated relative to the time of randomization (for no intervention group) / immunization (for nirsevimab group) and will be presented for those participants in All Randomized Set. If the concomitant medication is “Ongoing” at End of Study it will be indicated as such in the listing and the relative stop day will not be calculated. Only original dates will be presented in the listing even though the relative day may be based on an imputed date.

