In addition, all AE tables by SOC and PT listed above and flagged with (*) will also be repeated in participants who received other vaccines:

- ✓ On the same day as nirsevimab
- ✓ Within 7 days before or after nirsevimab immunization
- ✓ Within 14 days before or after nirsevimab immunization.

For the subgroups about participants who received other vaccines, see [Table 6](#) from Appendix 2 (Section 8.2) to get the vaccines to be considered.

Moreover, below tables will be produced:

- ✓ Non-serious TEAEs through Day 31 post-dosing/randomization by SOC and PT in at least 1% of participants
- ✓ Medically-attended TEAEs by SOC and PT in at least 1% of participants
- ✓ TEAEs through Day 7 post-dosing/randomization by SOC and PT
- ✓ TEAEs through Day 7 post-dosing/randomization by SOC and PT - Pyrexia
- ✓ TEAEs through Day 7 post-dosing/randomization by SOC and PT - Injection Site Reactions
- ✓ TEAEs through Day 14 post-dosing/randomization by SOC and PT
- ✓ TEAEs through Day 14 post-dosing/randomization by SOC and PT - Rash

Study Treatment Related Serious TEAEs tables by SOC and PT (overall and by subgroups) and with the number of events as well as 95% Clopper-Pearson confidence interval will also be produced at the time of Second Year Analysis in UK re-consented participants for the below periods:

- ✓ From 366 Days Post-Dosing/Randomization to 731 Days Post-Dosing/Randomization.
- ✓ From Day 1 to 731 Days Post-Dosing/Randomization
- ✓ From Day 1 to 366 Days Post-Dosing/Randomization

The summary table of TEAE will also be produced at the time of Second Year Analysis in UK re-consented participants for the below periods;

- ✓ From 366 Days Post-Dosing/Randomization to 731 Days Post-Dosing/Randomization.
- ✓ From Day 1 to 731 Days Post-Dosing/Randomization
- ✓ From Day 1 to 366 Days Post-Dosing/Randomization

For the period “From 366 Days Post-Dosing/Randomization to 731 Days Post-Dosing/Randomization”, only below TEAE will be presented:

- TEAE with a start date on or after Day 366,
- TEAE with a start date before Day 366 but ongoing at Day 366 (no stop date or with a stop date after Day 366).

For summaries by maximum intensity, participants with multiple TEAEs within a particular SOC or PT will be counted under the category of their most severe TEAE within that SOC or

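### The stop-date imputation rule is capped at a last dose date that is Day 1 for nirsevimab and does not exist for controls, and two medication definitions in SAP 6.4.3 leave gaps (minor)

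*SAP*

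**What the plan says.** SAP 5.2.3.2 states its aim first: dates are "imputed in a manner resulting in the earliest onset or the longest duration during the Treatment Period". Then: "For a missing / incomplete stop date the latest date of the following will be imputed", followed by three candidates: "The earlier date of the latest possible stop date and the date of last dose of treatment"; the earliest possible stop date; and the earliest possible start date. Records marked ongoing are not imputed. The parallel rule for start dates names an anchor in each arm, "the date of the randomization (for no intervention group) / immunization (for nirsevimab group"; the stop-date rule does not.

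The Protocol synopsis gives "Treatment Duration: 1 IM injection", and the second group receives nothing. SAP 5.1.3 ends the Treatment Period at the primary cut-off or the 12- or 24-month call (or 14 days after its due date), or at loss to follow-up or withdrawal. SAP 5.2.2 limits these imputations to deciding prior/concomitant status of medications and treatment-emergent status of adverse events. SAP 6.4.3 and 6.7.2.2 nevertheless let relative days in listings rest on imputed dates.

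On medications, SAP 6.4.3 says: "Prior medications are those taken prior to screening with a stop date prior to the date / time of randomization" (or immunization, in the nirsevimab group). Concomitant medications start on or after Day 1, or start earlier and stop on or after Day 1 or are ongoing. The table of medications around an LRTI admission has three criteria: a start inside the 14-day window, an earlier start with a stop inside it, or an earlier start with no stop date.

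**The concern.** A cap at the last dose suits a trial with repeated dosing, where that date lies near the end of treatment. Here it lies at the beginning, so the rule works against its own aim. For 14,430 of the 28,860 planned infants the date does not exist, and the SAP does not say what replaces it. Two programmers could both follow the text and classify the same control record differently.

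The two SAP 6.4.3 gaps do not arise from the imputation rule. They are definitions that fail to cover every record they are meant to cover, even when all dates are complete.

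**Working it through.** **Notation.** s = start date (known); e and L = earliest and latest possible stop dates; D1 = Day 1. The rule is

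imputed stop = max{ min(L, cap), e, s }, with cap = date of last dose. Feasible records have L ≥ s and L ≥ e.

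**Nirsevimab, start on or after Day 1.** The cap is D1. Since L ≥ s ≥ D1, min(L, D1) = D1 ≤ s, so the imputed stop is max(e, s). That is the earliest stop the record allows, hence the shortest duration. For earlier starts this is not always so, as record C shows.

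**Prior/concomitant status, start before Day 1.** The question is whether the imputed stop is on or after D1. For any cap at or after D1, min(L, cap) ≥ D1 exactly when L ≥ D1; if L < D1, all three terms are before D1. Status therefore depends only on L and is the same for a cap at Day 1, a cap at the end of the Treatment Period, or no cap. If the first term is set to missing, the rule becomes max(e, s). Status then changes whenever max(e, s) < D1 ≤ L.

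**Worked records.** Illustrative assumptions: D1 = 12 Oct 2022, consent 10 Oct 2022, last known date and end of Treatment Period 12 Oct 2023 (Day 366). A wholly missing stop then has e = 10 Oct 2022 (consent) and L = 11 Oct 2024 (last known date plus one year, taken as 365 days).

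| Record | Cap = Day 1 (nirsevimab as written; control if Day 1 is substituted) | Control, term ignored | Control, term missing | Cap = end of Treatment Period |
|---|---|---|---|---|
| A. AE starts 21 Oct 2022 (Day 10), stop wholly missing | 21 Oct 2022, 1 day | 11 Oct 2024, 722 days | 21 Oct 2022, 1 day | 12 Oct 2023, 357 days |
| B. AE starts 20 Nov 2022, stop `--DEC2022` | 1 Dec, 12 days | 31 Dec, 42 days | 1 Dec, 12 days | 31 Dec, 42 days |
| C. Drug starts 1 Sep 2022, stop `--OCT2022` | 12 Oct, concomitant | 31 Oct, concomitant | 1 Oct, prior | 31 Oct, concomitant |

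In record C the earliest possible stop is 1 Oct, so the Day 1 cap does not give the shortest duration there.

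**Enumeration.** Starts ran from 60 days before to 365 days after Day 1, against stops that were wholly missing, year only, or month and year in 2022–2023.
- Nirsevimab, start on or after Day 1: shortest possible stop in 4151 of 4151 combinations.
- Status, cap at Day 1 against cap at end of Treatment Period: 0 of 5299 differ.
- Control status with the term missing, against cap at end of Treatment Period: 180 of 5299 differ. These are the 60 start days before Day 1 times the three stop types that straddle it (wholly missing, 2022, October 2022): 60 × 3 = 180.

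These counts describe the grid and are not expected frequencies.

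**LRTI-admission table.** Count days from admission and read the second and third criteria as a start before day −14. A drug with a start before −14 and a recorded stop after +14 meets none of the three criteria, although it was taken throughout the window. On a grid of starts from −60 to 14 and recorded stops up to day 89, 7394 pairs overlap the window and 3944 are captured. The 3450 missed are all of this type (46 starts × 75 stops). Protocol 6.8 collects all medications given within 14 days before and after admission.

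**Prior medication.** SAP 5.1.2 runs screening from consent to Day 1, and the Protocol schedule of activities allows consent before Visit 1. A drug started after consent and stopped before Day 1 was not taken before screening, so it is not prior; it ended before Day 1, so it is not concomitant.

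**The case against.** The best defence is that SAP 5.2.2 confines these imputations to status, and for that purpose the Day 1 cap works: nirsevimab prior/concomitant status never changes. No summary of adverse-event duration is planned, so the shortened durations reach no planned table, only relative stop days in listings that also show the original dates. For controls there is a natural reading. SAP 5.1.1 defines Day 1 as randomization for controls and falls back on randomization when an immunization date is missing. On that reading both arms are treated alike. All of this stands, but the control reading has to be inferred, because the stop-date rule itself does not give it.

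The effect on treatment-emergent status is also close to empty. SAP 6.7.2.1 handles a missing stop date directly, and adverse events are collected only from dosing/randomization, so partly dated events that began earlier should be rare. The gap in the prior definition is narrow too: reportable drugs are tied mainly to adverse events, LRTI admissions and vaccines near Day 1, and a vaccine given between consent and Day 1 appears in its own 14-day table.

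A reader might infer that the cap also distorts the LRTI-admission medication table, or the carry-over of ongoing events into the Day 366 to Day 731 adverse-event table, differently by arm. The documents do not support this. Nothing in the SAP applies the imputed stop date to the LRTI window, and the gap there exists with fully recorded dates. The carry-over would be affected only if imputed stops were used for it, which SAP 5.2.2 appears to exclude.

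**Conclusion.** The point holds as a minor defect. The stop-date rule contradicts its stated aim for nirsevimab records starting on or after Day 1, and it is undefined for controls and for infants randomized to nirsevimab but not dosed. The one status consequence in the tables is for control records starting before Day 1 with a stop date that could fall on either side of it, and only if the absent term is treated as missing. The two gaps in SAP 6.4.3 are real and separate.

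It would be wrong to conclude that identical records are necessarily handled differently by arm, since two of the three control readings leave status the same. It would also be wrong to suspect the efficacy results. Under SAP 5.2.3.3 and 5.2.3.4, LRTI and wheeze end dates are not imputed, and the start-date rule they borrow does not use the last dose. The effect is confined to descriptive medication and safety tables and listings. Its size depends on how many stop dates are partial or missing, which the documents do not give.

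**What to change.** 1. In SAP 5.2.3.2, replace the date of last dose with the end of the Treatment Period as defined in SAP 5.1.3, for both arms. This meets the stated aim and leaves nirsevimab prior/concomitant status unchanged.
2. In SAP 6.4.3, define the LRTI-admission table as any medication whose start-to-stop interval overlaps admission ± 14 days.
3. In SAP 6.4.3, define prior medication as any medication with a stop date before Day 1, whatever its relation to screening.
4. Reconcile the restriction in SAP 5.2.2 with the use of imputed dates for relative days in SAP 6.4.3 and 6.7.2.2, and state whether imputed stops may enter the Day 366 to Day 731 table.

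For outputs already produced, document how the undefined control term was programmed. The cost is a few SAP sentences and minor reprogramming.

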5.2.3.3. Missing or Partial Dates for LRTI Hospitalization Start Dates

In case of missing or partial start dates of LRTI hospitalization, same rules as for AE will be applied. However, no substitution will be performed for missing or partial end dates of LRTI hospitalization.

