5.2.3.4. Missing or Partial Dates for Recurrent Wheeze Event Start/ Stop Dates

In case of missing or partial dates of Recurrent Wheeze Event, same rules as for LRTI Hospitalization will be applied.

5.2.4. Handling of Plasma / Blood / Serum Concentrations that are Below the Lower Limit of Quantification

Not Applicable.

6. Statistical Methods

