At the time of Second Year Analysis, incidence of RSV and all-cause LRTI hospitalization in UK reconsented participants only from 366 days post-dosing/randomization to 731 days post-dosing/randomization will be summarized by the treatment group. Descriptive statistics will be provided only.

Above analyses will be performed only in participants without the studied event before Day 366. In addition, number and percentage of participants with above events before and after Day 366 will be provided.

For UK reconsented participants who completed the study, the end date of the follow-up time will be the end of study date or the last available date with confirmation of no RSV/all-cause LRTI hospitalizations, whichever is earlier.

For UK reconsented participants who had contact for safety events after reconsented and discontinued from the study before Day 731, the end date of the follow-up time will be the last available date with confirmation of no RSV/all-cause LRTI hospitalizations.

For UK reconsented participants who had no contact for safety events at all after reconsenting, the end date of the follow-up time will be the consent date.

For UK reconsented participants who had no contact for safety events at all at the time of First Year Analysis but reported safety events with confirmation of no RSV/all-cause LRTI hospitalizations afterwards, the end date of the follow-up time will be the end of study date or last available date with confirmation of no RSV/all-cause LRTI hospitalizations, whichever is earlier.

Notes:

- If RSV/all-cause LRTI hospitalizations occur after Day 731, it will not be considered and then the end date will be Day 731.

- If a participant receives Beyfortus as part of a routine immunization, any RSV/all-cause LRTI hospitalization occurring after Beyfortus immunization but between Day 366 and Day 731 will not be considered and the end date will be the date of injection of Beyfortus.

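### The adverse-event earliest-onset rule, applied to missing or partial hospitalization and wheeze dates, can move second-year events out of the windows meant to detect second-season enhancement

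*SAP*

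**What the plan says.** SAP 5.2.3.3 on hospitalization start dates: "In case of missing or partial start dates of LRTI hospitalization, same rules as for AE will be applied". SAP 5.2.3.4: "In case of missing or partial dates of Recurrent Wheeze Event, same rules as for LRTI Hospitalization will be applied".

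The adverse-event (AE) rule in SAP 5.2.3.2 has dates "imputed in a manner resulting in the earliest onset or the longest duration during the Treatment Period". In its technical steps, "For a missing / incomplete start date the earliest date of the following will be imputed": (i) the later of the earliest possible start and randomization or immunization, (ii) the latest possible start, (iii) the latest possible stop. The earliest possible date is the first of the month if only the day is missing and 1 January if only the year is known. Otherwise it is "The day of informed consent, if the date is completely missing".

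SAP 5.2.2 limits the imputation of AE and medication dates to deciding treatment-emergent and prior/concomitant status. SAP 6.6 nevertheless invokes 5.2.3.3 and 5.2.3.4 for efficacy and notes that relative day and follow-up time may rest on an imputed date.

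On RSV and all-cause LRTI hospitalization from D366 to D731, SAP 6.6.4.3.6 states: "Above analyses will be performed only in participants without the studied event before Day 366". SAP 6.6.9.2.1 restricts its D366-511 and D512-731 analyses in the same way, to children with no studied event before D366 and D512 respectively.

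**The concern.** Choosing the earliest onset is cautious when the question is whether an AE is treatment-emergent. Here the question is which window an event belongs to, and the same choice errs in one direction: for any true event after Day 1, the imputed date is never later than the true date. A known discharge date is only an upper bound and cannot pull the start later. Contacts that had already confirmed the child event-free are ignored, although the SAP uses those dates for censoring.

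The second-year follow-up exists to look for antibody-dependent enhancement in the second RSV season (Protocol 4.2). A second-season admission dated into year 1 does not merely change window. It makes the child ineligible for the year-2 analysis, so both the event and the child disappear from it. Year-2 hospitalizations reach sites through a parental memory aid and calls at D546 and D731, and wheeze through retrospective record review, so incomplete dates are plausible.

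Two other parts of the documents fit poorly with the rule. SAP 5.2.3.1 uses mid-period values for partial birth dates, so earliest-date imputation is not a general convention. And an LRTI admission imputed to Day 1 sits badly with exclusion criteria E02 and E03, which bar active RSV infection or LRTI at randomization.

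**Working it through.** The plan gives no figure on this point, so the rule is applied as written.

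**Inputs.** Imputed start = min( max(earliest possible start, Day 1), latest possible start, latest possible stop ), from SAP 5.2.3.2. Relative day = date − Day 1 + 1 (SAP 5.1.1). Person-months = (end − start + 1)/30.4375 (SAP 6.6.1). Planned enrolment runs from 1 Sep 2022 to 28 Feb 2023 (Protocol 1.1), which is 181 days.

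**Single cases** (discharge date known in each):

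| Randomized | True admission | Recorded | Imputed | Consequence |
|---|---|---|---|---|
| 15 Oct 2022 | 10 Dec 2023, D422 | missing | 15 Oct 2022, D1 | out of D366-731 and D366-511; 1/30.4375 = 0.033 person-months |
| 15 Oct 2022 | 10 Dec 2023, D422 | 2023 | 1 Jan 2023, D79 | out of D366-731 and D366-511 |
| 15 Oct 2022 | 25 Oct 2023, D376 | Oct 2023 | 1 Oct 2023, D352 | out of D366-731 and D366-511 |
| 15 Oct 2022 | 10 Dec 2023, D422 | Dec 2023 | 1 Dec 2023, D413 | stays in year 2 |
| 15 Feb 2023 | 10 Dec 2024, D665 | 2024 | 1 Jan 2024, D321 | out of D366-731 and D512-731 |
| 15 Oct 2022 | 10 Oct 2024, D727 | 2024 | 1 Jan 2024, D444 | stays in D366-731, but moves from D512-731 to D366-511 |

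**General pattern.** A missing start date becomes Day 1 for every child. A year-only 2023 date becomes 1 January 2023 or Day 1 if later. That is always on or before 28 Feb 2023, so a true year-2 event in 2023 always leaves year 2. A year-only 2024 date becomes 1 January 2024, which is before D366 for children randomized from 2 Jan 2023: 58 of 181 enrolment days, or 32%. A month-and-year date crosses D366 only in the month that contains D366.

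**Shares.** Assume uniform enrolment over the 181 days and uniform true event days over D366-731, and count all day pairs. The second column restricts true events to October 2023-February 2024, an assumed second winter.

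| Recorded date | Moved before D366 | Same, second-winter events |
|---|---|---|
| missing | 100% | 100% |
| year only | 41% | 54% |
| month and year | 4% | 14% |

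These shares are conditional on the date being incomplete in that way. The documents do not say how often that happens.

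**Wheeze.** SAP 6.6.4.3.7 counts only episodes inside D366-731 and removes no child for an earlier one. A misdated episode is therefore lost from that window. Because recurrent wheeze needs two episodes, one lost episode can change the child's year-2 status, and the same episode can add to the count through D366.

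**The case against.** A reader might infer that second-season admissions would inflate first-season efficacy counts, or that the primary result is at risk. The documents do not support either reading.

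- Year-2 admissions are collected at the D546 and D731 calls. The season, D151 and D181 LRTI endpoints are analysed no later than the First Year Analysis and are not re-run at Second Year. On planned dates the last 12-month window closes on 28 Feb 2023 + 365 + 14 days = 13 Mar 2024, and the child randomized 15 Oct 2022 reaches D546 on 12 Apr 2024. The very earliest enrollees reach D546 on 28 Feb 2024, and no lock date is given, so overlap is not impossible; it is simply not shown.
- The SAP's document history dates the rule for partial LRTI and wheeze dates to version 5.0 (22 Apr 2024), after the Primary Analysis limit of 30 Apr 2023. The First Year re-run keeps the Primary Analysis rules.
- First and Second Year efficacy is descriptive.
- Admission and discharge dates come from medical records with source verification, so missing or year-only dates should be few. Listings show original dates, so imputed cases can be found.

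All of this stands and limits the reach of the point. It does not remove the year-2 problem: those analyses still lie ahead of the rule, their events are likely to be sparse, and the error runs one way.

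The phrase about the Treatment Period in SAP 5.2.3.2, read with the separate year-2 period in SAP 5.1.3, could be taken as a lower bound at D366. The technical steps contain no such bound, and that ambiguity also needs settling.

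**Conclusion.** The point holds for the second-year hospitalization windows. A missing or year-only admission date, or a month-and-year date in the boundary month, can move a true year-2 event before D366 or D512 and remove the child from the corresponding analysis. For wheeze the loss is of the episode, not the child; a reader who infers that wheeze children are dropped goes beyond SAP 6.6.4.3.7.

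Late first-year admissions can also move earlier in the First Year descriptive analyses. For example, an admission on 20 Mar 2023 in the child randomized 15 Oct 2022 becomes 1 Jan 2023 if only the year is recorded. As an illustration only, assume 44 versus 17 season events and equal person-time. Adding five misdated events to each arm takes efficacy from 1 − 17/44 = 61.4% to 1 − 22/49 = 55.1%, and the exact lower 95% limit from 31.0% to 24.3%, still above zero.

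The conclusion rests on the literal steps of SAP 5.2.3.2, and the shares rest on uniform enrolment and event days. The number of affected dates is unknown and probably small. The change is worth making because it is cheap and because one misplaced case can matter among few second-year events.

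**What to change.** Rewrite SAP 5.2.3.3 and 5.2.3.4 for start dates, and keep the AE rule for AEs and medications only:

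- Lower bound: the later of Day 1 and the last contact or record review that confirmed no such event.
- Upper bound: the earlier of the discharge date and the contact at which the event was reported.
- Impute the midpoint of that interval, restricted to any known month or year.
- Do not assign an ambiguous event to the window of the reporting contact. The 12-month call may run to D380, so that would push year-1 events into year 2.
- Report the number of imputed start dates by arm, and add a sensitivity analysis using latest possible dates for the year-2 windows.

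Check on the first case in the table: if the 12-month call on 15 Oct 2023 confirmed no event and discharge was 14 Dec 2023, the midpoint is 14 Nov 2023, D396, inside year 2.

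The cost is two SAP paragraphs, a small programming change and one extra table. Contact dates are already used to derive follow-up time. If the Second Year database is already locked, the counts and the sensitivity analysis can still be produced from existing data.
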